## A. Study Schema

#### **B.** Introduction

## **B.1.** Objectives

Describe the purpose, specific aims, or objectives of the study:

The purpose of this proof-of-concept study in humans is to determine if a noninvasive, ingestible device, called a "mini-pill", can collect gastrointestinal (GI) luminal content samples from 2 different locations along the GI tract after consumption of diets differing in protein source (meat and plant-based meat alternatives). The mini-pills will be recovered in the stool. We will analyze the microbial profile of the mini-pill contents and in stool, and also measure blood biomarkers related to cardiometabolic risk, to better understand the relationship between diet, microbiota and health.

## Specific aims:

- 1. To assess the feasibility of sampling GI luminal content from targeted regions in humans using the mini-pill and recovering the sealed mini-pills post-elimination in the stool.
- 2. To analyze and compare the luminal content microbial population (microbiota) recovered from two GI regions and in stool, after consumption of diets differing in source of protein (meat and plant-based meat alternatives).

#### Exploratory aim:

To compare the effects of diets containing meat and plant-based meat alternatives on metabolites in stool and blood biomarkers associated with cardiometabolic risk.

The ingestible mini-pill is a non-invasive, single-use, passive collection device that is not intended for diagnosis or treatment. The mini-pills have already been developed, tested and validated by two Tufts researchers, Drs. [name] (School of Engineering) and [name] (School of Veterinary Medicine), *in vitro*, *ex vitro*, and *in vivo* in animal models (*Supplement 1: Research Strategy and Supplement 2: Soft Autonomous Ingestible Device for Sampling the Small Intestinal Microbiome, Del-Rio-Ruiz R et al.*, *manuscript in review*). A NSR device designation is being sought from the IRB to conduct a 2-phase randomized-controlled double blind crossover trial in humans by providing two entrées per day containing either meat or plant-based meat alternatives for up to 3 weeks each. After 2 weeks on each diet, participants will consume a provided breakfast meal and then be asked to swallow 6 mini-pills along with a blue food coloring dissolved in 50 mL of water, return home and collect stool samples until all the mini-pills are recovered (varies between 2 and 4 days, but can be up to 6 days). This protocol will allow us to describe the diet-induced progressive change in the GI tract microbiota prior to and including that in the stool.

# **B.2.** Background and Rationale

1. Describe the relevant prior experience and gaps in current knowledge: The gut microbiota represents trillions of microogranisms and thousands of species. Among the various microbial communities associated with the human body, the GI tract microbiota is noted for its high concentration and species diversity, and is thought to play multiple systemic roles in health and disease In humans, the gut microbiota contribute enzymes not encoded by the host's genome and generate numerous bioactive compounds, such as short chain fatty acids (SCFA), secondary bile acids and trimethylamine (TMA) that elicit systemic metabolic effects. Dysbiosis (microbial imbalance) has been associated with conditions such as recurrent enteric infections, microbial overgrowth and a wide range of other disorders such as cardiovascular disease and type 2 diabetes. External influencers of the GI tract microbiota include diet, 9,10 as well as other environmental factors, such as physical activity, ambident temperature or medication. Considerable interest has settled on diet. 11,12

Most studies infer the state of the GI tract microbiome from the analysis of microbial communities in stool samples. Healthy dietary patterns, characterized as being relatively rich in minimally processed plant foods and dietary fiber, and poor in animal products and ultra-processed foods, have been associated with a low prevalence of chronic diseases such as cardiovascular disease and type 2 diabetes,  but the response of proximal intestinal microbial communities to diet is difficult to study. Whereas rapidly evolving DNA sequencing technologies have facilitated the analysis of complex microbial communities, our capacity to non-invasively sample luminal content from different locations along the GI tract has not evolved.

2. Rationale for the research and preliminary data: The mini-pill development and subsequent validation work was funded through a NIH R21 phased innovation mechanism. NIH R33 funding for the second phase, the proposed human trial, was contingent on successful completion of the *in vitro*, *ex vivo* and *in vivo* work in pigs and hounds. As part of the R21 phase of the proposal, we have successfully validated a 3D-printed sampling device, referred to as a *mini-pill*, to retrieve luminal content at pre-determined regions of the GI tract in pigs and hounds (*See Supplement 2: Soft Autonomous Ingestible Device for Sampling the Small Intestinal Microbiome, Del-Rio-Ruiz R et al., in review*).

The proposed study includes ingestion of six mini-pills per diet phase, three targeted to collect lumenal content from the upper GI, tract and three targeted to collect lumenal content from lower down in the GI tract. The rationale for three pills per location is to establish that sufficient qunatity of representative luninal content at each site is collected, and to determine reproducability. Sampling relies on uptake of intestinal content through the side inlets of the empty mini-pill as a result of natural GI peristalsis. Regional sampling of the mini-pill is initiated upon dissolution of the pH-sensitive enteric coating. Because the pH of the GI tract increases as the luminal content progresses from the duodenum to the colon, different pH-sensitive enteric material can be used to coat the mini-pills to sampling differ regions of the GI tract. Critical to minimizing contamination from downstream material, embedded absorbent beads located inside the mini-pill activate a valve which closes the intake inlet through which the sample has been acquired. (See Supplement 3: Minipill for Collection of GI Tract Luminal Content).

3. Significance of the research objectives: Because regions of the GI tract differ with respect to oxygen tension, pH and nutrient availability, the commonly sampled microbiota in stool is unlikely to reflect the microbial communities populating more proximal regions of the GI tract, particularly, the small intestine. To gain insights into the impact of the entire GI tract microbial environment on health and disease, it is essential to develop a methold to non-invasively sample luminal content from targeted locations, particularly upstream of the colon.

- 4. Specify if first time study device will be used in humans: This is the first time this speicifc 3D printed mini-pill device will be tested in humans. However, a similar NSR device, albeit larger (NCT05749068), has been tested in humans after receiving IRB approval at another institution (See Supplements 5 and 6). 
- 5. Is there an active control group?

☐ Yes No

# **B.3.** Risks to Subjects

List the reasonably foreseeable risks, discomforts, hazards, and/or inconveniences to the subjects related to their participation in the research, including risk of unintentional loss of confidentiality. There are no known risks associated with ingestion of the mini-pills. The results of in vivo safety testing of the minipills in hounds is provided in Supplement 2 (Soft Autonomous Ingestible Device for Sampling the Small Intestinal Microbiome, Del-Rio-Ruiz R et al., in review). A similar passive mini-pill has been tested in humans under non-significant risk designation after receiving IRB approval. Our mini-pill (6 mm x 15 mm housed in a 6.4 mm x 17.0 mm gel capsule) is smaller than the one studied by others (6 mm x 30 mm). Hence, is expected to have a lower risk during administration, GI-transit and excretion. The safety data for the prior study conducted in humans using a similar devise indicated "All devices safely exited all participants and were successfully retrieved. No adverse events were reported." Our mini-pill contains (i) no mechanical parts, motors or gears, (ii) no electronics, cables, antennas batteries or passive components, and (iii) no active or passive magnet or metal. The mini-pill is 3D-printed using biocompatible resins avoiding the risk for possible allergic reactions or exposure to toxins.

There are the rare risks of microscopic bleeding, obstruction, perforation, infection and potential for unknown risks from the mini-pill. In the event of suspected aspiration, additional diagnostic (e.g. chest x-ray) or therapeutic procedures (e.g. bronchoscopy) may be required and the participant will be referred by the study MD to the TMC Emergency Department for evaluation or the emergency department preferred by their primary care provider.

There are no major risks associated with the short-term consumption of the meat containing entrées. Prior work has reported no adverse effects from consumption of the plant-based meat alternatives. 16 Some of the plant-based alternative entrées contain gluten, so participants with known sensitivity to gluten will be excluded. There are no known risks associated with obtaining the study measures (height, weight, waist circumference and resting blood pressure). There might be some discomfort from fasting for 8 to 10 hours prior to the study visits. There may be some nausea associated with swallowing the 6 mini-pills. The need to collect and return multiple stool samples at the end of each diet phase, may be inconvenient for the participants. There is a low risk of sensitivity to Betty Crocker Classic Gel Food Color, which contains Blue 1. Most allergic reactions to blue dyes are mild, described as grade I (69– 87%) and present with urticaria (itchy skin), pruritus (hives), and/or generalized rash.  To address this issue participants with known sensitivity to food coloring will be excluded. Additionally, the nursing staff will monitor participants after ingestion of the pills and dye for any possible symptoms. There may be a small amount of bruising and discomfort, and rarely infection, associated with the drawing of blood samples. Subjects may become light-headed and faint. Every effort will be made to minimize discomfort to study subjects, with experienced nursing staff performing the blood draws. No known psychological or social risk are anticipated. There are no economic risks as study entrées will be provided to the study subjects, and there is no cost associated with the mini-pills. Protected health information will be collected as part of this study. Study participants may face risks related to inadvertent release of confidential information. This risk will be minimized through careful adherence to best practices for data collection and management. All research staff will be trained in principles and methods for assuring participant confidentiality and safety. Data will be used only in aggregate and no identifying

characteristics of individuals will be published or presented. Confidentiality of data will be maintained by using research identification numbers that uniquely identify each individual. Safeguards will be established to ensure the security and privacy of participants' study records. Databases will not use participants' names as identifiers. The files matching participants' names and demographic information with research ID numbers will be kept secure and only study personnel will have access to these files. After the study is completed, local data will be stored securely with other completed research studies.

- 1. State which study interventions may have unknown risks: None, reported by other investigators
- 2. State which study interventions may have risks to an embryo or fetus (if a subject is or becomes pregnant) or to a nursing infant of a study subject: 

  N/A
- 3. Describe risks to people other than the participating subject, e.g., risks to family members, friends, others or risks to the community: ⊠ N/A
- 4. Are there any risks to study investigators or staff performing the study procedures due to research with high risk populations (e.g. prisoners, intravenous drug users, patients with major psychiatric issues, etc.)? No

## **B.4. Potential Benefits to Subjects**

- 1. Describe the potential benefits that individual subjects may experience from taking part in the research. Include the probability, magnitude, and duration of the potential benefits. Discuss why the risks to subjects are reasonable in relation to the anticipated benefits to research subjects: 

  ☑ N/A, there is no direct benefit.
- 2. Describe any benefit to the population from which the subjects are drawn: The results of this study may allow for an advancement of our understanding about the relationship between diet, GI microbiome and health through development of a non-invasive methodology to analyze the intestinal microbiota from the duodenum to the colon.
- 3. Describe any benefit to science, society, and humanity in general: The results of this work may facilitate refinement of public health dietary guidance to optimize the microbiota throughout the GI tract for disease mitigation. This point is of particular importance as we shift towards personalized nutrition guidance. Ultimately, these types of studies, regardless of the diet comparison, can inform diet optimization with the intent of modifying the gut microbiota to improve long-term health outcomes.

#### **B.5.** Alternatives

- 1. Describe alternatives to participating in this research study (e.g. alternative treatments, no treatment (palliative care), participating in an activity without data being used for the research, etc.): Subjects may elect not to participate in the study.
- **2.** Describe the standard clinical care that may be an alternative:  $\boxtimes N/A$
- 3. Describe how the subject can receive the research procedures/drug/device used in this study in a non-research setting: N/A

# C. Enrollment and Withdrawal

#### C.1. Inclusion Criteria

- 1) Men and postmenopausal women
- 2) Age  $\geq$ 50 to  $\leq$ 75 years
- 3) BMI >20 to <35 kg/m^2
- 4) Normotensive with or without medication
- 5) Normal gastrointestinal function with regular bowel movements at least once every other day
- 6) Normal kidney and liver function
- 7) Willingness to swallow the mini-pills
- 8) Willingness to collect and return multiple stool samples
- 9) Adequate refrigerator and freezer space to store study entrées
- 10) Intent to remain in the greater Boston area during the intervention periods

#### C.2. Exclusion Criteria

- 1) Individuals self-reporting adhering to any type of vegetarian diet
- 2) Lack of willingness to restrict fish intake to less than once per week during the dietary intervention phases
- 3) Allergy/intolerance/religious reasons to avoid study foods or food ingredients, including known hypersensitivity to Blue 1 food coloring and wheat gluten.
- 4) Regular use of prebiotics or probiotics within the past 3 months
- 5) Regular use of laxatives or fiber supplements
- 6) Chronic constipation
- 7) Chronic use of antibiotics (except topical)
- 8) Regular use of stomach acid lowering and weight loss medications such as GLP-1 agonists
- 9) Use of dental prophylaxis
- 10) Planned colonoscopy 2 months prior to or during the study period
- 11) Gastroparesis
- 12) Swallowing disorder, or inability or difficulty taking pills
- 13) Malabsorptive and inflammatory bowel disease, diverticulosis, and history of diverticulitis, gastric/esophageal/intestinal surgery, including lap banding or bariatric surgery.
- 14) History of bowel obstruction, pancreas and liver disorders.
- 15) Any form of active substance abuse or dependence (including drug or alcohol abuse). This information will be stored in REDCAP in a subsection that has no identifiers.
- 16) Established major chronic diseases such as cardiovascular disease, diabetes, active cancer within the last 5 years, or any significant medical condition at the study MD's discretion
- 17) A clinical condition that, in the judgment of the study MD or principal investigator, could potentially pose a health risk to the subject while involved in the study.
- 18) Unwillingness to adhere to study protocol
- 19) Intent to increase or decrease body weight during the study period
- 20) No Social Security number (for payment and IRS forms).
- 21) Individuals who directly report to any member of the research team.

Can study subjects participate in another research study while participating in this research study:

#### ⊠ No

*Please explain your response if needed:* Introduction of additional diet and/or lifestyle interventions can affect the study outcomes. If participation in another research study involves blood draws in addition to those associated with this study, total may exceed allowable amounts.

## C.3. Screening and Eligibility

1. Describe in detail the methods that will be used to identify potential subjects and how the eligibility criteria will be assessed and satisfied. Specify what type of screening will take place prior to informed consent and screening that will take place after informed consent:

Eligibility criteria will be determined via a prescreening questionnaire administered over the telephone, and an in-person screening visit that includes measurement of blood pressure, waist circumference, and height and weight to determine BMI. Additionally, at the screening visit, a nursing team member will review medical history and medication use to confirm eligibility. Dietary screening by a registered dietician will be conducted to determine food aversions, food allergies and/or sensitivities that would interfere with acceptability of the study entrées. The participant will be provided with a stool collection kit and must successfully provide a stool sample within 48 hours of screening to confirm regular bowel movements, as well as to familiarize themselves with the stool collection protocol after mini-pill ingestion.

- 2. State who will confirm eligibility and ensure that eligibility and consent were documented prior to the subject receiving any study intervention. Note that those who are designated to determine eligibility must have appropriate training, expertise, and oversight, for example a physician PI or Co-I on a biomedical study: Each subject's file will be reviewed by the PI, study doctor or designate prior to beginning the study to confirm eligibility and to ensure the Informed Consents were signed and the subject understands the study procedures.
- 3. Will a screening data collection form/log be used in this research study? \( \square\$ No

# C.4. Withdrawal of Subjects

- 1. Describe anticipated circumstances under which subjects will be withdrawn from the research without their consent: Non-compliance with study protocol based on not attending pre-scheduled study visits, not providing blood or stool samples, not picking up and consuming provided study entrées, change in medical status or use of steroids or oral antibiotics during the study. Additionally, if a subject does not follow all of the HNRCA volunteer rules and regulations, they will be withdrawn from the study without their consent.
- 2. Describe procedures that will be followed when subjects either withdraw voluntarily or are withdrawn from the research, including the possibility of partial withdrawal from study intervention with continued data collection. If a participant wishes to withdraw part-way through the study they are at liberty to do and no further data will be collected. Samples and data that have already been collected will be analyzed as per protocol.
- 3. Describe any necessary safety precautions to be applied to subjects who withdraw or are withdrawn (tapering drug doses, evaluative x-ray, etc.):  $\boxtimes N/A$

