Week 1\_Day 1: Following the screening visit, participants will come to the HNRCA after an 8 to 10 hour fast to return their stool sample. They will then be given the opportunity to review and sign the Study Informed Consent form and also be given the option to review and sign the Optional Tissue Banking Informed Consent form. Once enrolled, participants will have their weight, waist circumference, and blood pressure measured and provide a fasting blood sample. They will meet with a registered dietician to review instructions for entrée storage/consumption and pick up diet phase I specific entrées and checklist.

Week 2\_ Day 8: Participants will come to the HNRCA to pick up another week of study entrées and also return and review their Entrée Checklist with a registered dietician.

*Week 2-Day 14:* Participants will come to the HNRCA after an 8 to 10 hour fast to provide a fasting blood draw. They will be given a breakfast containing a study entrée specific to the diet phase to be consumed within 30 minutes, and then asked to swallow 6 mini-pills along with blue dye dispersed in ½

\*\*The number of stool samples to be collected will vary depending on mini-pill recovery

cup of water within 15 minutes. Additional water may be consumed, if desired. Participants will be given study entrées for another week and stool collection kits with cooler and instructions.

*Week 3-Days 15 to 21:* Participants will continue to consume 2 entrées per day until the mini-pills are eliminated in the stool, which can vary between 2 and 4 days, but can be up to 6 days. Participants will be asked to collect and return all stool samples produced every 48 hours, until they are informed by study staff that all pills have been recovered.

Participants can stop consuming the entrées once all mini-pills are recovered. There will be a 2 week break at this point during which participants will have no study obligations and can consume their normal diet. If all of the mini-pills are not recovered after 6 days, participants can stop consuming the study entrees, and we will conduct a 2-week follow up telephone call to inquire about symptoms or concerns.

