#### **Diet Phase II**

Week 6\_Day 36: Participants will come to the HNRCA after an 8 to 10 hour fast to provide a fasting blood sample and have their weight, waist circumference, and blood pressure measured. They will pick up diet phase II specific entrées and checklist.

Week 7\_ Day 43: Participants will come to the HNRCA to pick up another week of study entrées and also return and review their Entrée Checklist with a registered dietician.

Week 7-Day 49: Participants will come to the HNRCA after an 8 to 10 hour fast to provide a fasting blood draw. They will be given a breakfast containing a study entrée specific to the diet phase to be consumed within 30 minutes and then asked to swallow 6 mini-pills along with blue dye dispersed in ½ cup of water within 15 minutes. Additional water may be consumed, if desired. Participants will be given study entrées for another week and stool collection kits with cooler and instructions.

Week 8-Days 50 to 56: Participants will continue to consume 2 entrées per day until the mini-pills are eliminated in the stool, which can vary between 2 and 4 days, but can be up to 6 days. Participants will be asked to collect and return all stool samples produced every 48 hours, until they are informed by study staff that all pills have been recovered. Participants can stop consuming the entrées once all minipills are recovered. If all of the mini-pills are not recovered after 6 days, participants can stop consuming the study entrees, and we will conduct a 2-week follow up telephone call to inquire about symptoms or concerns.

Additional Study Procedures: Participants will complete one 24-hour dietary recall at the beginning of the first diet phase (baseline) and then two at the end of each diet phase over the phone. On day 1, a member of the HNRCA Dietary Assessment Unit will provide instructions and give participants a two-dimensional measuring aid (Food Amounts Booklet) to assist with estimating portion size. The first dietary recall will be completed by phone within 24 hours. Thereafter, they will be contacted by phone to complete additional 24-hour dietary recalls.

a. Procedures, situations, or materials that may be hazardous, and the precautions to be exercised to maintain subject safety: N/A.

Please also describe the following concerning procedures:

[figure not shown]

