a. How individuals will be screened for eligibility. Specify screening that will take place prior to informed consent and screening that will take place after informed consent: IRB approved telephone prescreening questionnaire will be used to determine eligibility based on inclusion and exclusion criteria (see sections C.1 and C.2). Participants who meet prescreening criteria will be invited to the HNRCA for a screening visit to confirm eligibility. At the screening visit,

after obtaining consent, BMI will be confirmed by direct measurement of height and weight. In addition, blood pressure will be measured, and medical history/medication use and dietary habits will be reviewed.

- b. *Procedures being performed to monitor subjects for safety or to minimize risks:* Every effort will be made to minimize discomfort to study subjects, with experienced nursing staff performing the blood draws and monitoring mini-pill ingestion. Post ingestion of the minipills, all participants will receive a 2 week follow up telephone call. During this call, we will review medical history in order to monitor any possible longer-term side effects including urgent/emergency visits, or hospitalizations specifically for abdominal pain/discomfort, GI obstruction, perforation, diverticulitis, GI bleeding.
  - c. All drugs and devices used in the research, their regulatory approval status (whether they are approved by the FDA and being used within their FDA approved indication), and the purpose of their use. For drugs, specify the dosage of each drug, how they will be administered, and how often they will be administered. For devices, specify how they will be used/implanted:

The mini-pill is a size 2 pill. It is not a wearable. It is not an implant. The mini-pill does not deliver any drugs. It is not intended for diagnosis or treatment. It is a passive, single-use, ingestible collection device that is recovered from the stool and its contents will be analyzed for microbial communities inhabiting the GI lumen. See Supplement 3 (Ingestible Mini-pill for Collection of GI Tract Luminal Content) which provides a detailed description, images, dimensions, designs and the safety profile of the device from both materials and our recent animal studies in hounds. An image of the pill is shown below.

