## F.6. Provisions to Monitor the Study to Ensure the Safety of Subjects

- 1. Describe the plan to periodically evaluate the data regarding both harms and benefits to assess subject safety as follows:
  - a. The data that will be reviewed, including safety data, untoward events, and efficacy data: The study subject will be monitored for discomfort during the study visit and will be accompanied at all times by a research team member. There are no medically anticipated immediate adverse effects associated with the assessments (height, weight, waist circumference, blood pressure) taken at the study visit, with consumption of the food items, or oral ingestion of the mini-pills.

Who will review the data: The study doctor will evaluate any GI or other issues reported by participants. An independent physician, [name]. Professor of Medicine and Nutrition, Tufts Medical Center/Tufts University will act as Safety Monitor and will review AEs and SAEs, if they occur and sign off on annual safety reports to the NIH.

- b. How the safety information will be obtained and documented (e.g., case report forms, by telephone calls with participants, printouts of laboratory results, etc.): Any instances of GI discomfort/side effects self-reported by participants to MRU staff via phone or at an inperson visit will be documented in REDCap.
- c. The frequency of data collection, including when safety data collection starts: If nursing staff determine a report is an AE or has potential of being an AE, the study doctor will review and the PI or designee will be sent a summary of the complaint/issue by email on the day the report has been made to the IRB and Safety Monitor.
- d. *The frequency or periodicity of review of cumulative data*: Yearly.
- e. The statistical tests for analyzing the safety data to determine whether harm is occurring: N/A
- f. Any conditions that trigger an immediate suspension of the research or other action for the research: N/A

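### The withdrawal rule in C.4 makes no exception for people who have swallowed mini-pills: it ends recovery tracking for those who choose to leave and leaves unclear whether the 2-week safety call still happens

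*Protocol*

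**What the plan says.** Section C.4 has two relevant answers. Item 2, on voluntary withdrawal, reads "If a participant wishes to withdraw part-way through the study they are at liberty to do and no further data will be collected"; it adds that material already in hand will still be analysed. Item 3 asks for any "necessary safety precautions to be applied to subjects who withdraw or are withdrawn" and is marked N/A. Item 3 covers both voluntary and forced withdrawal; the stop on data collection in item 2 is written for voluntary withdrawal only.

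Other sections describe what follows ingestion:

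- B.2, item 4 says that this device has not been used in humans before.
- B.3 acknowledges the hazards: "There are the rare risks of microscopic bleeding, obstruction, perforation, infection and potential for unknown risks from the mini-pill".
- E.2 (Days 15 to 21 and Days 50 to 56) asks participants to "collect and return all stool samples produced every 48 hours, until they are informed by study staff that all pills have been recovered". If pills are still missing after 6 days, "we will conduct a 2-week follow up telephone call to inquire about symptoms or concerns".
- E.2, item b, on safety monitoring, says that after ingestion "all participants will receive a 2 week follow up telephone call", in which "we will review medical history in order to monitor any possible longer-term side effects including urgent/emergency visits, or hospitalizations".
- F.6, item 1b records "Any instances of GI discomfort/side effects self-reported by participants to MRU staff via phone" or at a visit, and the study doctor evaluates such reports.
- H.1, item 2 names recovery of the 12 mini-pills as the safety endpoint.

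**The concern.** The physical risk from a swallowed device does not end when a person leaves the study. The protocol treats stool tracking and a call at 2 weeks as warranted after ingestion, yet its withdrawal section stops data collection and plans no precaution, without separating those who have pills inside them from those who have never swallowed one.

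Two things are at stake. The first is the safety of someone who leaves with a pill unaccounted for in a first-in-human device study. The second is the safety endpoint: once stool return stops, a pill that passed unseen cannot be told apart from a retained one, so recovery is unknown for that person.

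Some exits may themselves be related to the device. C.4, item 1 lists a change in medical status and failure to provide stool among the grounds for forced withdrawal. The first could be a complication; the second removes the only recovery route the protocol describes.

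**Working it through.** No power or error-rate figure is involved. The check is schedule arithmetic plus a reading of the sections side by side.

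**Inputs.** Ingestion on Day 14 and Day 49, six pills each time (E.2 and Table 1); stool tracking of at most 6 days after ingestion (E.2); a call at 2 weeks, that is 14 days (E.2, item b); a 2-week call if pills are missing after 6 days (E.2, both phases).

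**Last day of stool tracking** = ingestion day + 6.
- Phase I: 14 + 6 = Day 20
- Phase II: 49 + 6 = Day 55

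**Safety call of E.2, item b** = ingestion day + 14.
- Phase I: 14 + 14 = Day 28
- Phase II: 49 + 14 = Day 63

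**Missing-pill call.** E.2 does not say from when its 2 weeks are counted. Counted from ingestion, it coincides with the call above. Counted from the 6-day limit:
- Phase I: 20 + 14 = Day 34
- Phase II: 55 + 14 = Day 69

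**Pills possibly unrecovered at exit:** up to 6 per ingestion, and 2 × 6 = 12 over the study, which matches the endpoint in H.1.

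**What each kind of exit means, as written**

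| Element | Voluntary exit after ingestion | Forced exit after ingestion |
|---|---|---|
| Stool tracking (to Day 20 / Day 55) | Ended by C.4, item 2 | Neither continued nor barred; C.4, item 3 plans nothing |
| 2-week call to all participants (about Day 28 / Day 63) | Unclear: E.2 promises it, C.4 stops data collection | Not barred; not confirmed |
| Missing-pill call | Unclear, for the same reason | Not barred; not confirmed |
| Self-report and study-doctor review (F.6) | Remains | Remains |

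The two windows should be kept apart. Loss of recovery tracking is possible only in the first 6 days after each ingestion, and E.2 expects most recoveries within 2 to 4 days. From then until the call, only the call is in doubt.

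**Number affected.** The protocol gives no count of exits by study day, so none is calculated.

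**The case against.** The best defence is that E.2, item b is the specific safety provision and is unconditional once pills are swallowed, while C.4, item 2 answers a general question about continued data collection. On that reading C.4 ends research data only and the call survives. This reading is tenable. A reader might infer that the protocol flatly contradicts itself, or that withdrawers certainly lose the call; the text supports neither. E.2 does not mention withdrawal and C.4 does not mention the call, so what stands is that staff cannot tell which governs.

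It can also be said that the N/A is less odd than it looks. Even for people who stay, the only stated step for missing pills is to stop the entrées and receive a call, so a person who leaves loses at most that call and the knowledge of whether the pills passed. That limits the size of the point. But the item asks directly about precautions on withdrawal, and the plan already contains two that fit.

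Three more points on that side hold. Safeguards remain: the study doctor evaluates reported symptoms and an independent Safety Monitor reviews adverse events. They depend on the participant getting in touch, however, and do not show whether pills passed. Leaving may be rare, since C.5.4 pays nothing for a phase left partway and little is asked of participants after recovery. And the consent pages are not shown, so wording on contact after withdrawal may exist there.

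**Conclusion.** The point holds as a gap in a stated rule, and as a cheap safety improvement. For voluntary withdrawal, C.4 read literally ends pill-recovery tracking for up to 6 days after each ingestion and leaves both 2-week calls in doubt. For forced withdrawal it plans no precaution but does not bar follow-up.

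Three stronger conclusions might be drawn and are not supported:

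- That withdrawers have no safety cover. Self-report with study-doctor review continues, and the call to all participants may survive.
- That the E.2, item b call is the only scheduled contact about symptoms. E.2 also describes a missing-pill call, which may be the same contact or a later one.
- That up to half the participants are exposed, from 60 enrolled for 30 completers. H.2 counts everyone who signs a consent form as enrolled, including at screening, and nothing says when people leave. The number leaving after ingestion may be small or zero.

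The conclusion assumes that C.4 is followed as worded and that no unseen document supplies the exception. It does not touch the sample size, the error rate or the microbiota analyses; its only analytic effect is unknown recovery for those who leave during tracking.

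**What to change.** Replace the N/A in C.4, item 3 and add a matching exception to item 2, along these lines: anyone who has swallowed at least one mini-pill and then withdraws or is withdrawn will be offered, with their permission, (a) continued stool return until all pills are recovered or until day 6 after ingestion, whichever comes first, and (b) the 2-week post-ingestion call described in E.2, item b. Reported symptoms or unrecovered pills are referred to the study doctor.

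The cost is a few extra stool kits and calls of a kind the plan already includes, and matching consent wording. The offer compels no one, so recovery stays unknown for people who decline.
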